8.4 UNANTICIPATED PROBLEMS

8.4.1 DEFINITION OF UNANTICIPATED PROBLEMS (UP)

Unanticipated problems involving risks to participants or others will include, in general, any incident, experience, or outcome that meets all of the following criteria:

- Unexpected in terms of nature, severity, or frequency, given a) the research procedures that are described in the protocol-related documents, such as the IRB/EC-approved research protocol and informed consent document; and b) the characteristics of the participant population being studied;
- Related or possibly related to participation in the research (“possibly related” means there is a reasonable possibility that the incident, experience, or outcome may have been caused by the procedures involved in the research); and
- Suggests that the research places participants or others at a greater risk of harm (including physical, psychological, economic, or social harm) than was previously known or recognized.

For this study, UPs include⁴³:

- **Unanticipated adverse device effect (UADE)**⁴⁴ – any serious adverse effect on health or safety or any life-threatening problem or death caused by, or associated with, a device, if that effect, problem, or death was not previously identified in nature, severity, or degree of incidence in the investigational plan or application (including a supplementary plan or application), or any other unanticipated serious problem associated with a device that relates to the rights, safety, or welfare of subjects.
- **Serious health threat** is a signal from any adverse event or device deficiency that indicates an imminent risk of death or a serious deterioration in the health in subjects, users or other persons, and that requires prompt remedial action for other subjects, users or other persons⁴⁵.

⁴³ Per the recommendation in the US FDA “Guidance for Clinical Investigators, Sponsors, and IRBs Adverse Event Reporting to IRBs - Improving Human Subject Protection” (§§ III.B and IV), and in agreement with 21 CFR §§ 812.46(b), 812.150(a)(1), 812.150(b)(1) and § 9.2.5 of ISO 14155:2020.

⁴⁴ Refer to 21 CFR 812.3(s). Consistent with the language defining the unanticipated serious adverse device effect (USADE) in § 3.42 of EN ISO 14155:2011/AC:2011 and § 3.51 of ISO 14155:2020.

⁴⁵ § 3.46 of ISO 14155:2020

	The efficacy of a frequency-tuned electromagnetic field treatment in facilitating the recovery of subacute ischemic stroke patients – a pivotal study		
	No. BQ5	Ver. 4	Page 77 of 150

NOTE: This would include events that are of significant and unexpected nature such that they become alarming as a potential serious health hazard or possibility of multiple deaths occurring at short intervals.

8.4.2 UNANTICIPATED PROBLEM REPORTING

An Investigator shall submit to the Sponsor and, if required, to the reviewing IRBs/ECs (and, where applicable, regulatory authority) a report of any unanticipated problem occurring during an investigation⁴⁶. The Sponsor will conduct evaluation of unanticipated problems⁴⁷ and report the results of such evaluation to regulatory authorities and to all reviewing IRBs/ECs and participating Investigators.

If an UADE presents an unreasonable risk to subjects, the Sponsor shall terminate all investigations or parts of investigations presenting that risk as soon as possible. Termination shall occur not later than 5 working days after the Sponsor makes this determination and not later than 15 working days after the sponsor first received notice of the effect. The Sponsor will not resume a terminated investigation without IRB/EC and the U.S. FDA approval⁴⁸.

The results of Sponsor's evaluation of unanticipated problems will be reported to the U.S. FDA and to all reviewing IRB's and participating Investigators within 10 working days after the Sponsor first receives notice of the effect⁴⁹. Thereafter the sponsor shall submit such additional reports concerning the effect as FDA requests.

8.4.3 REPORTING UNANTICIPATED PROBLEMS TO PARTICIPANTS

Not applicable.

9 STATISTICAL CONSIDERATIONS

9.1 STATISTICAL HYPOTHESES

– **Null hypothesis:**

Mean change in mRS score from baseline (post-stroke day 4-21) to the end of study visit (90 ±15 days post-stroke) in the BQ 2.0 group = mean change in the sham group.

⁴⁶ Timelines for reporting to the Sponsor are outlined in § 8.3.6. For IRB reporting in the United States, Investigators should follow the timelines delineated in 21 CFR812.150(a)(1).

⁴⁷ 21 CFR 812.46 and § 7.4.4 of ISO 14155:2020

⁴⁸ 21 CFR 812.46 and § 8.2.1 of ISO 14155:2020

⁴⁹ 21 CFR 812.150(b)(1) § 7.4.4 of ISO 14155:2020

	The efficacy of a frequency-tuned electromagnetic field treatment in facilitating the recovery of subacute ischemic stroke patients – a pivotal study		
	No. BQ5	Ver. 4	Page 78 of 150

– **Alternative hypothesis:**

Mean change in mRS score from baseline (post-stroke day 4-21) to the end of study visit (90 ±15 days post-stroke) in the BQ 2.0 group ≠ mean change in the sham group.

9.2 SAMPLE SIZE DETERMINATION

A sample size is calculated to test the null hypothesis with 80% power at a 5% two-sided level of significance using a two sample-t-test for simplicity, even though the main statistical analysis may employ a statistically more powerful model-based approach. The estimates used for the mean and standard deviation of the changes from baseline to day 90 are taken from the literature as well as company pilot study data. In the pilot study, the mean change in mRS score from baseline to week 9 in the treatment group was -2.5 (SD=0.66) versus -1.3 (SD=0.46) in the sham group. In the literature a difference of 0.06 points on the mRS between treatment groups is considered clinically meaningful (114). As powering the trial to detect this difference would yield infeasibly large sample sizes, sample size projections were based on detecting a difference as low as 40% of the difference seen in the pilot trial = 0.5-point. To detect a 0.5-point difference between the groups with 80% power at a 5% level of significance using a standard deviation of 1 point and 1:1 allocation ratio, the calculated sample size (PROC POWER in SAS V9.4) is 128 participants in total, 64 participants in each arm. Allowing for a 15% dropout, 150 participants should be randomized.

9.3 POPULATIONS FOR ANALYSES

The following analysis sets are defined for this study:

- Intent-To-Treat (ITT) Analysis Set – will consist of all subjects randomized. In accordance with the ITT principle, all subjects randomized will be kept in their originally assigned treatment group.
- Modified ITT Analysis Set (mITT) – will consist of all subjects from ITT analysis set for whom treatment was initiated and will be analyzed as randomized.
- Per-Protocol Analysis Set (PP) – includes all subjects from the mITT analysis set who have no significant protocol deviations (examples of such potential protocol deviations are listed in § 7.2), were treated for a minimum of 20 completed sessions, with data available for the analysis (defined as at least one data point post baseline) and will be analyzed as treated.
- Safety Analysis Set (SAF) - will consist of all subjects where treatment was initiated, with subjects analyzed as treated.

The SAF analysis set will serve as the principal analysis set for the analysis of safety.

	The efficacy of a frequency-tuned electromagnetic field treatment in facilitating the recovery of subacute ischemic stroke patients – a pivotal study		
	No. BQ5	Ver. 4	Page 79 of 150

The mITT analysis set will serve as the principal analysis set for efficacy assessments (including for secondary endpoints).

Efficacy assessments (including for secondary endpoints) will also be performed on the PP as well as the ITT analysis set as a sensitivity analysis.

9.4 STATISTICAL ANALYSES

9.4.1 GENERAL APPROACH

Statistical analyses will be performed using SAS® v9.4 or higher (SAS Institute, Cary, NC, USA). Statistical analyses and reporting will be performed in compliance with FDA Guidance E6 and E9 and ISO 14155;2020.

Study data will be summarized with descriptive statistics and presented in tables and figures. Continuous variables will be summarized by a mean, standard deviation, minimum, median, and maximum and categorical variables by a count and percentage. For comparison of continuous variables, the two-sample t-test or the Wilcoxon rank sum test will be used as appropriate. For comparison of proportions (categorical variables), the chi-squared test or Fisher's exact test will be used as appropriate. A Cochran-Armitage trend test may be used when the response is ranked. For comparison of time to event data, the log-rank test will be used. If multiple measurements are taken in a single subject, statistics described below will be appropriately modified to accommodate the within subject correlation.

Detailed methodologies of the statistical analyses of the data collected in this study will be outlined in a trial-specific Statistical Analysis Plan (SAP). Any changes to planned analyses will be described and justified in the SAP. Analyses outlined in the SAP take precedent over those defined in the protocol to the extent there are any conflicts between the two documents.

Significance Levels and Type I Error

The overall significance level for this study is 5% using two-tailed tests, except for the group by site interaction that will be tested at a significance level of 15%.

The hierarchy (stepwise gatekeeper) approach will be adopted for the primary and secondary endpoints to control type I error due to multiple endpoint testing.

The primary endpoint will be analyzed first and only if the null hypothesis is rejected at a 5% level of significance or lower then we shall continue to test the secondary endpoints in a hierarchical manner. Nominal p-values will be reported, even if eventually due to the hierarchy the result is not considered statistically significant.

	The efficacy of a frequency-tuned electromagnetic field treatment in facilitating the recovery of subacute ischemic stroke patients – a pivotal study		
	No. BQ5	Ver. 4	Page 80 of 150

The hierarchical order of analysis of the secondary endpoint family will be:

1. Lead secondary endpoint: FMA-UE (upper limb motor impairment) – change from baseline (4-21 days post-stroke) to 90 days post-stroke.
2. BBT (upper extremity function) – change from baseline (4-21 days post-stroke) to 90 days post-stroke.
3. 10MWT (gait speed) – change from baseline (4-21 days post-stroke) to 90 days post-stroke.
4. SIS Hand Domain (patient-reported hand function) – change from baseline (4-21 days post-stroke) to 90 days post-stroke.
5. SIS-16 (patient-reported physical functional limitation) – change from baseline (4-21 days post-stroke) to 90 days post-stroke.
6. EQ-5D-5L (health-related quality of life) at 90 days post-stroke.

9.4.2 ANALYSIS OF THE PRIMARY ENDPOINT

The primary endpoint, mRS change from baseline (day 4-21 post-stroke) to 90 days post-stroke, will be compared between the treatment groups using repeated measures analysis of covariance (ANCOVA, SAS® MIXED procedure).

The model will include the following fixed effects: treatment group, visit [categorical – midterm follow-up visit (± 4 days from 20th treatment) and Day 90 follow-up visit (day 90 ± 15 days post-stroke)], treatment group by visit interaction with baseline mRS and age entered as covariates. Age will be entered as a continuous variable so that the potential for co-linearity problems will be minimized. Center will be entered as a random effect. The treatment group by site interaction will be evaluated as well, but not as part of the principal statistical evaluation.

The compound symmetry covariance structure will be used. If the model does not converge, then either the unstructured or autoregressive (AR1) (whichever model has the lower Akaike information criterion statistic) covariance matrix structure will be used instead. At this time point (up to 3 months post stroke), we do not expect a high proportion of dropouts, as a placebo effect of the sham treatment is expected and was taken into consideration in the design of the study. Thus, any missing data at this time point can be considered missing at random. Therefore, since likelihood based repeated measures is also an imputation method, for this evaluation no other method of imputation of missing data is considered beyond the model estimates. Nevertheless, should the missing at random assumption prove to be incorrect, a sensitivity analysis using methods for data imputation may be performed, such as last observed value (LOV) of that endpoint (115). The LOV is defined as the last available post baseline visit data up to and including the last treatment visit or termination visit. Additionally, we may consider multiple

	The efficacy of a frequency-tuned electromagnetic field treatment in facilitating the recovery of subacute ischemic stroke patients – a pivotal study		
	No. BQ5	Ver. 4	Page 81 of 150

imputation using a model incorporating key baseline prognostic features as well as the last post-randomization if deemed necessary.

The principal statistical analysis will be a comparison between the treatment groups, derived from the visit by treatment group interaction term from the model. The adjusted mean change from baseline in mRS scores at the 90 days post-stroke visit will be estimated from the model (LS Means) interaction term for each group as well as for the difference between the adjusted means and presented together with 95% confidence intervals and level of significance.

The null hypothesis will be rejected in favor of the alternative hypothesis and the study deemed successful if the P value is <0.05 and the mean change mRS in the BQ 2.0 group is higher than that of the sham group at the 90 days post stroke visit.

A shift analysis of the primary endpoint will be performed as a sensitivity analysis as well.

Handling of Missing Primary Endpoint Data

By the 90 days post-stroke visit, we do not expect a high proportion of dropouts, as a placebo effect of the sham treatment is expected and was taken into consideration in the design of the study by using conservative estimates of the treatment effect.

All subjects with at least 1 post-baseline measurement will be included in the statistical analyses. The primary endpoint will be analyzed using a likelihood based repeated measures model, which can handle data missing at random.

For the mITT set, missing primary outcome data at day 90 will be imputed with multiple imputation using a model incorporating key baseline prognostic features as well as the last post-randomization observed value (LOV) of that endpoint (115). The LOV is defined as the last available post baseline visit data up to and including the last treatment visit or termination visit. The LOCF imputation method will also be used to carry forward the most recent data prior to withdrawal/dropout as a sensitivity analysis.

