National Institutes of Health Stroke Scale (NIHSS) score		X					
Transcription of last mRS score given as part of routine care prior to discharge from ACH		X ¹²					
Transcription of blood count ¹³	X						
Provision of imaging data ¹⁴¹⁵	X						
Complete case report forms		X	X	X	X	X	X

¹¹ In women of childbearing potential, a urine or a blood test, or based on official medical documentation.

¹² To be retrieved after consenting; this score will not serve as the baseline mRS score.

¹³ Limited to transcription of red blood cell distribution width and absolute white cell count values from the blood count performed at the time of admission into the Intensive Care Unit (ICU) or ACH (the earlier available of the two).

¹⁴ Provision of Digital Imaging and Communications in Medicine (DICOM) files obtained from all computed tomography (CT), CT angiography (CTA), CT perfusion (CTP), and brain magnetic resonance imaging (MRI) perfusion/diffusion-weighted imaging (DWI/PWI) / fluid attenuated inversion recovery brain magnetic resonance angiography (FLAIR), and brain magnetic resonance angiography (MRA) studies available from the first 7 days in the ACH.

¹⁵ If multiple images are available from different days/recording sessions at the acute stay, collect the first image (must) and the last image. MRI images are preferred over CT

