Importantly, the effect of acute ischemic stroke treatments upon final 3-month disability outcome is determined by early clinical and imaging outcomes at 24-96 hours. At least 8 multicenter trials and registries studies, enrolling a collective total of 10 494 acute ischemic stroke patients treated with supportive care, IV thrombolysis, and/or endovascular thrombectomy have found that the dominant independent early predictors of 3-month disability outcome are patient age, extent of neurologic deficits at 24-48 hours on the NIHSS, and infarct extent at 24-48 hours (35-42). Reperfusion therapy has no independent influence on the trajectory of patient recovery, in terms of disability, from 48 hours to day 90 (35).

The initial evaluation and management of ischemic stroke patients in ACHs typically lasts between 2-9 days (median 4-5 days). Ischemic stroke patients are then discharged to one among a range of continued care settings, including their own homes, IRFs), and skilled nursing facilities (SNFs; (43)). The standard of care for ischemic patients in the subacute and chronic stages has two main elements. The first is medical and surgical therapies to prevent recurrent stroke, including administering anti-thrombotic agents and controlling key modifiable risk factors. The second is rehabilitation therapy to maximize recovery from the index stroke. Rehabilitation therapies are functional and impairment-specific, focusing on the areas of loss which are individual to each patient (44).

In the case of motor impairment, one of the most common and devastating deficits after stroke, extensive OT and PT regimens are regularly implemented, focusing on individual areas of gross and fine motor impairment. PT/OT typically involves a variety of specific motor skill exercises, mobility training, range of motion therapy and constraint-induced mobility therapy (CIMT). The recommendation is that physical rehabilitation be initiated as early as is tolerated after the first 24 hours from stroke onset (19). The intensity of therapy depends on patient ability as well as treatment setting. There is strong evidence for benefit from PT/OT interventions involving highly intensive and highly repetitive task-oriented and task-specific training (20). CIMT has been found to be moderately effective and recommended as part of PT/OT regimens for appropriate patients (45).

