Direct motoric and cognitive interaction with a physical and occupational therapist remains the mainstay of rehabilitation therapy for residual motor impairment in the United States. Among ischemic stroke patients with a moderate to severe disability at the end of the acute care hospital

phase, multiple studies have demonstrated the typical subsequent course is some improvement in deficits over the next 3 months followed by stabilization at a permanent level of functioning. Multiple studies have shown that, with standard rehabilitative care, moderately-severely disabled patients improve by a mean of around 1.1 points on the mRS scale by day 90 (46-48). Taking into account this improvement, the mRS level at the conclusion of acute care, upon stabilization from acute injury is strongly and consistently correlated with mRS at day 90 (49). This improvement is consistent across broad patient groups, regardless of age, sex, and ischemic stroke mechanism. However, this improvement is typically incomplete, and most patients are then left with residual, permanent disability.

Some technologies have been tested, generally in small trials, for potential to further improve recovery above this standard of care, including neuromuscular electrical stimulation (NMES), functional electrical stimulation (FES), and robot-assisted therapy (50, 51). Although of some promise, none of these devices has been yet demonstrated to be unequivocally beneficial and none are deemed to be elements in the current standard of care in the United States (43).

In sum, although there are demonstrated benefits of select acute ischemic stroke therapies and PT/OT rehabilitation programs for stroke, a substantial majority of stroke patients, roughly 90% (2), are left with persisting, lifelong impairments despite receiving the current standard of care. Thus, while the standard of care may be effective and allow for a meaningful reduction in disability, for those patients with a moderate to severe disability, these changes are often insufficient. In these patients, a chronic disability persists, not allowing them to return to work or participate in their usual pre-stroke activities.

Potential role of the investigational device

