5 STUDY POPULATION

5.1 INCLUSION CRITERIA

In order to be eligible to participate in this study, an individual must meet all of the following criteria:

1. mRS score of 3 or 4.
2. FMA-UE score between 10-45 (inclusive) of impaired limb.
3. Age 22 to 85 years of age (inclusive).
4. Diagnosed with an ischemic stroke, confirmed by CT²¹ or MRI²² imaging.
5. Four to 21 days from stroke onset (or last known well).
6. Pre-stroke mRS of 0 or 1.
7. Able to sit with the investigational device for 40 consecutive minutes, in the opinion of the investigator or designee.
8. Can follow a 3-step command, such as “take the paper, fold it in half, and return it to me”.
9. Willingness to participate in occupational/physical therapy activities during study intervention sessions.
10. Availability of a relative or other caregiver able to assist during PT/OT treatment, and to operate an application installed on a mobile device, including a video call.
11. If female, not pregnant (as confirmed by a urine or a blood test, or as determined by an official medical document) or breastfeeding and with no ability to become pregnant or on an acceptable method of contraception during the study
12. Informed consent signed by subject (if competent) or legally authorized representative.

²⁰ 42 CFR Part 11 § 11.10(a)(3) “completion date” or “primary completion date” synonymous to the “completion date” defined in section 402(j)(1)(A)(v) of the Public Health Service Act [42 U.S.C § 282(j)(1)(A)(v)]

²¹ Computed tomography

²² Magnetic resonance imaging

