5.2 EXCLUSION CRITERIA

An individual who meets any of the following criteria will be excluded from participation in this study:

1. Severe neglect impairment (NIHSS item 11, score = 2) or neglect that is severe enough to interfere with reasonable performance of study procedures.
2. Implanted active electronic or passive MR-incompatible devices.
3. Previous ischemic or hemorrhagic stroke within 2 weeks before the index stroke.
4. Pre-existing neurological condition (eg, Alzheimer's disease, Parkinson's disease, multiple sclerosis, traumatic brain injury, spinal cord injury) or physical limitation that would interfere significantly with the subject's participation in the study and/or confound neurological or functional evaluation.
5. Active epilepsy or currently taking anti-epileptic medication (indicated for the treatment of a seizure disorder), or seizure in the last 5 years
6. Significant visual disturbances that cannot be corrected and that would interfere significantly with the subject's participation in the study and/or confound neurological or functional evaluation.
7. Unstable serious illness/condition (eg, active cancer, severe heart failure, active psychiatric condition) or life expectancy of less than 12 months.
8. A known severe allergic reaction to acrylic-based adhesives.
9. Ongoing alcohol abuse and/or illicit drug use.
10. Participation in another trial that would conflict with the current study or clinical endpoint interference may occur.
11. Employee of the Sponsor.
12. Prisoner.

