8.1.1.2 SCREENING & ENROLLMENT, BASELINE VISIT

Efforts should be made to complete enrolment, randomization and initiate treatments as early as possible within the window of recruitment, and target to complete a first treatment within 4 weekdays from admission to the participating site.

For consented subjects, the following additional data will be recorded at this visit:

- Demographics – age, sex, race/ethnicity
- Medical history - presence of concomitant medical conditions (eg, hypertension, diabetes, hyperlipidemia, atrial fibrillation, prior ischemic stroke, prior hemorrhagic stroke, current or past smoking)
- Vital signs – temperature, pulse, blood pressure.
- Concomitant medications – any concomitant medications by or administered to the subject at the time of screening (for details, refer to § 6.5).
- In women of childbearing potential a urine or blood test will be performed unless there is a documentation of a negative pregnancy test in an official medical documentation.
- mRS
- FMA-UE,
- BBT,
- 10MWT
- SIS Hand Domain,
- SIS-16,
- SAFE
- NIHSS
- Any adverse events

Consented subjects, who are 4 to 21 days post-stroke, and have passed screening for eligibility will advance to the treatment phase of the study, commencing with randomization.

Randomization should be performed within 24 hours from the mRS and FMA-UE assessments. If more than 24 hours have elapsed, these assessments should be repeated and only those subjects whose reassessed scores for both assessments conform with the eligibility criteria will be randomized. The later scores will serve as the baseline scores and for stratification.

Eligible subjects will be randomly assigned, at a 1:1 allocation ratio, to either the active or sham study intervention groups.

The following additional data will be obtained after randomization and not later than Midterm follow-up visit:

	The efficacy of a frequency-tuned electromagnetic field treatment in facilitating the recovery of subacute ischemic stroke patients – a pivotal study		
	No. BQ5	Ver. 4	Page 63 of 150

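### The primary model adjusts for a two-level baseline mRS, age and center but omits baseline NIHSS, forgoing a plausible precision gain at very small cost

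*Protocol*

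**What the plan says.** **Model.** Protocol section 9.4.2 specifies a repeated-measures ANCOVA with treatment group, visit and "treatment group by visit interaction with baseline mRS and age entered as covariates". Age is continuous and center is a random effect. NIHSS does not appear.

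**Range of the severity covariate.** Inclusion criterion 1 (section 5.1) requires an "mRS score of 3 or 4", so baseline mRS takes two values in this trial.

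**Availability of NIHSS.** The schedule of activities (section 1.3) places the "National Institutes of Health Stroke Scale (NIHSS) score" at the Screening, Enrollment & Baseline visit. Section 8.1.1.2 lists it among the items introduced by "For consented subjects, the following additional data will be recorded at this visit", and randomization follows. The data that section allows to be obtained after randomization are imaging and two blood-count values. Exclusion criterion 1 (section 5.2) uses one item of the scale: "Severe neglect impairment (NIHSS item 11, score = 2".

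**Prognostic value.** Section 2.2 says the "dominant independent early predictors of 3-month disability outcome are patient age, extent of neurologic deficits at 24-48 hours on the NIHSS", together with infarct extent. The same section says mRS at the end of acute care is "strongly and consistently correlated with mRS at day 90".

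**Sample size.** Section 9.2 uses an unadjusted two-sample t-test and remarks that "the main statistical analysis may employ a statistically more powerful model-based approach".

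**The concern.** The three adjustment terms (center, age, baseline mRS) correspond to the three stratification factors in section 6.3.1, so the model uses no prognostic information beyond what stratification already handles. Severity enters only as a 3-versus-4 indicator, which leaves differences within each level to the residual. Of the three early predictors that section 2.2 singles out, age is used, infarct imaging is collected after randomization, and NIHSS is scheduled at the baseline visit but unused, with no reason given.

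What is at stake is the width of the confidence interval for the day-90 difference, and so the power of a trial planned with 64 evaluable patients per arm. A baseline covariate that explains residual variance buys precision without any new data.

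**Working it through.** **Inputs from the protocol.** Section 9.2: difference 0.5, SD 1, two-sided 5%, 64 per arm (128 evaluable). Section 9.4.6: maximum 292 evaluable (146 per arm), effect about 0.33.

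**Assumption.** The protocol gives no partial R-squared for NIHSS given mRS, age and center. Values of 0, 0.05, 0.10 and 0.20 are shown.

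**Step 1: the plan's own figure.** The noncentrality is 0.5 / (1 × √(2/64)) = 2.828. With 126 df, noncentral-t power is 80.1%. With 63 per arm it is 79.5%. So 64 per arm is reproduced.

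**Step 2: add one covariate, net of its cost.** Take SD 1 as the residual SD before NIHSS is added. The residual variance becomes (1 − R²), multiplied by 1 + 1/124 = 1.0081 for chance imbalance in the new covariate, with 125 df. Half-width is t × √(variance × 2/64). Equivalent N is 128 / variance.

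| Partial R² | Variance | Power | 95% CI half-width | Equivalent N |
|---|---|---|---|---|
| not added | 1.000 | 80.1% | 0.350 | 128 |
| 0 | 1.008 | 79.8% | 0.351 | 127 |
| 0.05 | 0.958 | 81.8% | 0.342 | 134 |
| 0.10 | 0.907 | 83.8% | 0.333 | 141 |
| 0.20 | 0.806 | 87.8% | 0.314 | 159 |

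**Step 3: break-even.** The variance falls once (1 − R²) × 1.0081 < 1, that is R² > 1 − 1/1.0081 = 0.008, a partial correlation of about 0.09.

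**Step 4: maximum sample size.** At 146 per arm and difference 0.33, power is 80.2% without NIHSS. With it, using 1 + 1/288 = 1.0035 and 289 df, power is 80.1%, 82.1%, 84.1% and 88.0% for the same four R² values. Break-even is about 0.35%.

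**Step 5: a less favorable reading of SD 1.** Section 9.2 gives SD 1 for an unadjusted t-test. Suppose mRS and age already explain 20% of that variance (an assumption). The planned model then has variance 0.80 and power 88.1%. Adding NIHSS at partial R² 0.05 gives variance 0.80 × 0.95 × 1.0081 = 0.766 and power 89.4%. At 0.10 it gives 0.726 and 90.9%. The gains are 1.3 and 2.8 points, against 1.7 and 3.7 in Step 2 (81.8 − 80.1 and 83.8 − 80.1).

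**The case against.** **The model is valid as written.** It carries every stratification factor and the endpoint's own baseline value. This stands. A reader might infer that omitting NIHSS biases the comparison or leaves the trial short of its stated power. The protocol supports neither: randomization protects the estimate, and the 80% rests on an unadjusted t-test that needs no covariate.

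**The evidence that NIHSS helps here is indirect.** Section 2.2 concerns NIHSS at 24-48 hours, while the trial scores it at day 4-21 in patients limited to mRS 3-4 and FMA-UE 10-45, with severe neglect excluded. These limits probably narrow its range. Section 2.2 also reports that mRS after stabilization already tracks day-90 mRS closely. This stands too: the gain is plausible, not established, and no R² in the table has an anchor in the protocol. Against it, mRS has only two levels in this trial, which leaves room for a finer severity score.

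**A complete score is not guaranteed.** It is tempting to infer from exclusion criterion 1 that every randomized patient has an NIHSS total. The criterion needs item 11 only. Section 8.1.1.2 requires mRS and FMA-UE to be repeated when more than 24 hours old but sets no such rule for NIHSS. A mixed model drops a patient whose covariate is missing, and the break-even of 0.8% is about one patient in 128. The remedy therefore needs a missing-data rule.

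**The SAP may add the covariate.** Section 9.4.1 gives the SAP precedence, and it is not available here. The point concerns the list that the protocol itself states. FMA-UE is another baseline candidate; NIHSS is preferred here because section 2.2 names it.

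**Conclusion.** The point holds as a forgone efficiency. The protocol names its covariates, limits severity to a two-level mRS, and leaves out a baseline score whose acute-phase counterpart it describes as a leading predictor of the outcome.

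With SD 1 as the residual SD and a partial R² of 0.05 to 0.20, power at 128 evaluable patients would rise from 80.1% to 81.8-87.8%, equivalent to about 6 to 31 more evaluable patients (134 − 128 and 159 − 128). If mRS and age already explain 20% of the variance, the rise is from 88.1% to 89.4-90.9% for partial R² 0.05-0.10. The loss if NIHSS adds nothing is about 0.3 point. The trade is asymmetric in favor of adding it, provided that missing scores do not remove patients. The size of the gain rests wholly on the assumed R².

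**What to change.** Before the interim analysis is unblinded:

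- Add baseline NIHSS total score to the section 9.4.2 model as a prespecified continuous covariate, alongside baseline mRS, age and random center.
- State that the same model supplies the effect estimate for conditional power at the interim and for the final test. Section 9.4.6 defines the interim effect as a difference in mean change without saying whether it is adjusted.
- Prespecify a rule for missing baseline NIHSS, for example single imputation from baseline data blind to treatment arm, so that no randomized patient is dropped from the model for lack of the score.

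The cost is one model degree of freedom, a short change of wording with one added rule, and about 0.3 percentage point of power in the worst case. No new data are collected and the sample size does not change.
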